# **Study Population**

a. The study population will be adult patients older than 18 with severe knee osteoarthritis that have failed non-operative conservative therapy and now require total knee arthroplasty. All patients will undergo unilateral primary total knee arthroplasty with the Zimmer Persona prosthesis performed by [name].

Pre-operative clearance will be done by the Montefiore Geriatrics team prior to day of surgery. Inclusion criteria: Adult patients with knee osteoarthritis who have failed conservative therapy and undergoing elected TKA.

Exclusion criteria:

i. <18 years old

ii. Any patient with pacemaker or any electrical stimulator device

- iii. Significant baseline deformity (flexion contracture)
- iv. Patient with clinically diagnosed fibromyalgia?
- v. Patients without capacity to consent for the study
- vi. Patients not able to have local nerve block or spinal anesthesia
- vii. Patients with prior opioid use

viii. Patient who is categorized to have `Severe` fear and anxiety responses to pain, according to the PCS survey.

# b. Power/sample size

We will need a sample of 50 subjects in each group to have 80% power to detect a 30% reduction in mean 48 hour opioid use at a two-sided 0.05 significance level, assuming a mean 48 hour opioid use of 84.2mg and a standard deviation of 44.7 in the standard of care group. For this study, we anticipate to start with 25 patients per group.

Drop out/loss to follow up rate: If any patient who is assigned to treatment group decides to leave the study for any reason or any point of the study, they will be dropped out of study. Similarly, if the patient does not show up to post-operative follow up, they will be dropped from the study. The post-op follow up rates are almost at 100%, so we do not anticipate to have more than 10% drop-off. After any potential drop-offs, we aim to have 20 subjects per group at the end of this study.

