# Study Design:

It will be a prospective, randomized, single-blinded study. The study device will be used for only 2 days during the post-surgery hospital stay. The patients will be followed until their 6 weeks post-op office visit. We aim to finalize the study in 6 months.

Before enrollment into the study: During their pre-operative visit, patients will fill out a short questionnaire (The Pain Catastrophizing Scale, PCS short form) to assess their eligibility for the treatment and create a homogenized group of patients. Inclusion criteria is detailed below. 50 patients who are eligible for the study will be enrolled by written consent. Informed written consent will be obtained by PI ([name]) and the health care professional team ([name] and [name],PA ) during pre-operation office visit.

Once the patient volunteers to enroll to the study, we will establish their patient-specific intensity during their pre-op office visit. We will plan to have patient establish their correct and comfortable intensity before their surgery. The device comes in a carrying case with all the set supplies. At the time of placement, a health care provider will place the pre-packaged sterile electrode roughly 7-10 cm above and below the knee for testing or just above and below the

dressing during on the operated knee. Each set of electrodes will then be connected via a lead wire to the stimulation device.

Establishing the correct and comfortable intensity before operation will be as follows: The stimulation device which has a large power button will be turned on but provide no initial signal intensity. The patient will then be instructed to use the "plus" arrow on the device to slowly increase the signal intensity. The goal is to reach a point of intensity that feels strong but comfortable. The best method is to continue to increase to the point where it becomes slightly uncomfortable and the patient may experience some muscle fasciculations. Once that point is reached, decrease the intensity slightly and then use that intensity for their treatment. This patient specific intensity will be recorded and used for the IFC treatment.

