The outcomes will be monitored in the immediate post-operative period by the Orthopaedic Surgery clinical team at Wakefield Hospital as well as at during the first post-op visit by [name] office by physician assistant ([name],PA) and nurse practitioner ([name]). The average hospital stay for TKA patients in the hospital (Wakefield) varies between 48-72 hours post-operatively. Typically, patients have a follow-up visit at 2 weeks and 6 weeks after surgery in the Hutchinson Campus, Tower 1 Orthopaedic Surgery Department clinic.

1. Primary outcome will be the post-operative pain medication usage during the first 24 and 48 hours. Daily opioid use will also be accounted based on electronic medical record reported by the patient's nurse after providing the patient with the specific medication. In addition, patients will be asked to rate their pain based on a set VAS pain scale twice a day before the IFC treatment.

2. Secondary outcomes Fitness for discharge on postoperative day 1and day 2 this will be measured utilizing the AM-PAC "6-Clicks" Basic Mobility Inpatient Short Form. The "6-Clicks" tool measures functional ability by having an assessor rate a patient's ability to perform physical tasks such as turning over in bed, moving from a bed to chair, and climbing steps. Scores are tallied to a total of 24 possible points, giving a quantitative measure of a patient's ability to perform these tasks. We will also use the `time` to reach the discharge as the outcome, pain scores recorded by nursing and physical therapy, complications, and any 30-day post discharge emergency department ED visits. Range of motion will be recorded during the daily physical therapy sessions by PT professionals with a goniometer. Range of motion then be assessed again in clinic at the first post-operative visit. Edema- thigh circumference will be calculated at the superior pole of the patella both prior to the surgery and daily post-operatively.All these outcome scores are done routinely as standard of care and they are recorded in patients charts in EPIC.

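### The only power figure (80%) is for 50 per group, but the trial enrols 25 and aims to finish with 20, where power for the same effect is about 50% and 41%

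*Combined protocol and SAP*

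**What the plan says.** Study Population, b. Power/sample size, states: "We will need a sample of 50 subjects in each group to have 80% power to detect a 30% reduction" in mean 48-hour opioid use. The inputs are two-sided 0.05, a mean of 84.2 mg and an SD of 44.7 under standard of care. The next sentence reads "For this study, we anticipate to start with 25 patients per group". Study Design agrees with the smaller number: "50 patients who are eligible for the study will be enrolled by written consent", and "We aim to finalize the study in 6 months".

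The same sample-size section expects little loss, "so we do not anticipate to have more than 10% drop-off", yet concludes "After any potential drop-offs, we aim to have 20 subjects per group at the end of this study". It also sets a removal rule: "if the patient does not show up to post-operative follow up, they will be dropped from the study". The primary outcome is pain medication use over the first 24 and 48 hours, and its source is given in Study Design: "Daily opioid use will also be accounted based on electronic medical record".

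Data and Safety Monitoring, 4. Data analysis, states an efficacy hypothesis, a 0.05 significance level, summaries by mean, SD and range, and a t-test or Mann-Whitney test. It plans no confidence interval.

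**The concern.** The 80% describes a trial twice the planned enrolment and two and a half times the target number of completers. A reader, ethics board or funder could take it as the power of this trial. Saying that the study will start with 25 leaves open whether more will follow, but no second stage, interim look, sample-size re-estimation or continuation rule is described.

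If the true effect is the one the plan chose to detect, the trial is about as likely to miss it as to find it. With no interval planned, a non-significant p-value would be the main result, and it could be read as showing that the treatment does not work.

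Two details of the loss text add to this. A 10% ceiling on loss and a target of 20 from 25 do not correspond. And the removal rule can discard primary-outcome data already collected in hospital because of a visit weeks later.

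**Working it through.** **Inputs from the plan.** Control mean 84.2 mg; SD 44.7; 30% reduction; two-sided alpha 0.05; power 80% (all from b. Power/sample size); 1:1 allocation (Randomization). The SD is given only for standard of care. I assume it holds in both arms and test that below.

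**Target difference.** 0.30 × 84.2 = 25.26 mg; standardised, 25.26/44.7 = 0.565.

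**Reproducing the plan's figure.** Normal approximation: n = 2 × (1.960 + 0.842)² × (44.7/25.26)² ≈ 49.2, so 50 per group. The exact t-test calculation gives 50.1, so 51, with power 79.9% at 50. The stated 50 is correct.

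**Same effect at the planned sizes.** SE = 44.7 × √(2/n), noncentrality = 25.26/SE, df = 2n − 2, power from the noncentral t distribution. The detectable difference is the one giving 80% power. The half-width is t(0.975, df) × SE.

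| n per group | SE (mg) | Noncentrality | Power | Detectable at 80% power | 95% CI half-width (mg) |
|---|---|---|---|---|---|
| 50 (stated need) | 8.94 | 2.83 | 79.9% | – | – |
| 25 (enrolled) | 12.64 | 1.998 | 49.9% | 36.1 mg (43%) | 25.4 |
| 22.5 (10% loss) | 13.33 | 1.895 | 45.7% | 38.2 mg (45%) | 26.9 |
| 20 (end target) | 14.14 | 1.787 | 41.4% | 40.6 mg (48%) | 28.6 |

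The 22.5 is an average; 22 and 23 per group give 45% and 47%.

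Put another way, an observed difference of exactly 25.26 mg with the assumed SD gives p = 0.051 at 25 per group, 0.065 at 22.5 and 0.082 at 20. This restates the power result and is not a separate harm.

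**Sensitivity.**
- Normal approximation: 51.5% at 25 and 43.1% at 20.
- Mann-Whitney test with normal data (relative efficiency about 0.955): about 48% and 40%.
- SD in the treated arm falling with its mean (0.7 × 44.7 = 31.3, an assumption): the averaged SD is √((44.7² + 31.3²)/2) ≈ 38.6, and power is about 62% and 52%. This reading would give 90% power at 50 per group, so it is not the one behind the plan's 80%.

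**Loss figures.** 25 × 0.9 = 22.5 remaining; ending with 20 implies 1 − 20/25 = 20% loss.

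**The case against.** Nothing in the section is miscalculated. The need for 50 and the intention to start with 25 stand in adjacent sentences, and the Monitoring section itself mentions low enrolment, so the small size is not hidden. That is fair: the fault is a size without a power or a justification, not a wrong sum. But visibility does not supply the power that applies.

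The wording about starting with 25 might imply a first stage. No later stage is described, and the same section sets 20 per group as the target for the end of the study.

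The claim of no better than an even chance depends on a common SD. This stands as a qualification: with a smaller SD in the treated arm, power could reach about 62% at 25 per group, still far below 80%.

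The 10% and the 20 per group can be read as an expected ceiling on loss and a cautious floor. That reading is possible, but the text should say so. With follow-up expected to be nearly complete, the removal rule may cost few patients.

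Finally, stays average 48 to 72 hours, so someone discharged before 48 hours may lack a complete in-hospital total. Retention therefore protects the data that exist; it does not guarantee a full total for every randomised patient.

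**Conclusion.** The concern holds. The plan's only power statement does not apply to the trial it describes. On the plan's own inputs with a common SD, which is the reading that reproduces its 50 per group, power for a 30% reduction is 49.9% at 25 per group, about 46% after 10% loss and 41.4% at 20. Reductions of about 43% to 48% would be needed for 80% power. A smaller SD in the treated arm (0.7 × 44.7) raises power to about 62% and 52%, and a Mann-Whitney test lowers it slightly; no version examined comes near 80% at the planned sizes. The loss wording and the removal rule are secondary, but they point the same way and are easily corrected. This needs correcting before the plan is relied on.

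**What to change.** In b. Power/sample size, replace the sentence on the starting size with wording such as:

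> This study will randomise 25 patients per group, which is its final size. Assuming a common SD of 44.7 mg, this gives about 50% power to detect a 30% reduction in 48-hour opioid use (46% with 10% loss, 41% with 20 per group analysed). Power of 80% is available only for a reduction of about 43% to 48%.

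If 25 is not the final size, say so and state the rule for continuing. Give the reason for the chosen size, and align the loss figures: 10% leaves 22 to 23 per group.

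In 4. Data analysis, add that the difference in 48-hour opioid use will be reported with its 95% confidence interval and that a non-significant result is not evidence of no effect. State also that in-hospital opioid data already collected stay in the primary analysis when a patient misses a later clinic visit, subject to any withdrawal of consent.

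This costs wording only and makes the stated power less favourable. It discloses the shortfall without removing it.

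The alternative is to enrol what the plan says it needs. Allowing for 10% loss, 50/0.9 = 55.6, so 56 per group: 112 in total, 62 more than planned, and probably longer than 6 months. If missed visits no longer cost primary data, the number lies closer to 50 or 51 per group (100 to 102 in total, 50 to 52 more).

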## **Randomization**

Prior to surgery in the clinic visit, patients will be given the The Pain Catastrophizing Scale, PCS short form. Based on the results of surveys, we will only include patients with Mild or Moderate anxiety towards pain. Eligible patients will be asked if they would enroll in the study. The survey will allow the opportunity to find a homogenized patients group for treatment and control groups.

Enrolled patients will be randomly selected into `IFC treatment` or `Control` groups after their surgery. This will enable us to eliminate any possible surgical bias.

We will use block randomization for this study: the surgeon and study group will not interfere in the randomization process to eliminate possible bias. Participants will be randomized in a 1:1 ratio (treatment:placebo). A block randomization scheme with a block size of 6 will be generated and maintained by the study statistician. The statistician will provide the sites with a set of randomization envelopes to be used in the study clinics. The randomization envelopes will be stored by the study coordinators in a locked cabinet. Study staff, not including the investigator who will perform clinical evaluations after surgery, will assign these envelopes in sequential order, by envelope number, to eligible participants. Each randomization envelope will include study treatment arm randomization assignment. Assignment of the randomization envelope is considered the effective act of participant enrollment/randomization.

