# 4. Data analysis

We hypothesize that IFC therapy will improve patient's pain management and range of motion as well as decrease soft tissue edema after TKA when compared to control group. Study variables: total opioid consumption per 24h and 48h, VAS pain scale, KOOS pain score, range of motion, thigh circumference, 6-click AMP scores.

The significance level of the test was targeted at 0.05.

All outcomes and PT exam measures will be summarized as mean, standard deviation, and range. Differences between means will be analyzed with a Student's t-test or Mann-Whitney U test.

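### The drop-out rule, with no analysis set defined, reads as a completers analysis, although most dropped patients will already have 48-hour opioid data in the chart

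*Combined protocol and SAP*

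**What the plan says.** The rule is in the combined protocol and SAP, Study Population, b. Power/sample size, in the paragraph on drop-out and loss to follow-up. It has two parts. The first covers withdrawal: "If any patient who is assigned to treatment group decides to leave the study for any reason or any point of the study", that patient is dropped. The second covers missed visits: "if the patient does not show up to post-operative follow up, they will be dropped from the study". The paragraph argues from near-complete post-operative attendance, "so we do not anticipate to have more than 10% drop-off", and then states that after losses "we aim to have 20 subjects per group at the end of this study", from a start of 25.

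Four other places bear on it:

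- **Study Design, primary outcome.** The outcome is pain medication use in the first 24 and 48 hours. On its source: "Daily opioid use will also be accounted based on electronic medical record".
- **Study Design, hospital stay and visits.** The average stay "varies between 48-72 hours post-operatively", and clinic visits follow at 2 and 6 weeks.
- **Randomization.** Patients are allocated after surgery, and "Assignment of the randomization envelope is considered the effective act of participant enrollment/randomization".
- **4. Data analysis.** "All outcomes and PT exam measures will be summarized as mean, standard deviation, and range", followed by a t-test or Mann-Whitney test. It names no analysis set and gives no rule for missing data or for data recorded before a patient leaves.

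**The concern.** The rule ties membership of the study to events that can come weeks after the primary outcome is complete. A patient who finishes 48 hours in hospital, has every opioid dose charted and then misses a clinic visit is dropped, although nothing is missing from that patient's primary outcome. Because the envelope fixes enrolment, every such loss is an exclusion after randomisation.

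Two things are at stake. One is information: the trial starts at about 50% power and would discard usable observations. The other is comparability: if patients who leave the IFC arm use more opioid than those who stay, removing them makes IFC look better than it is. The withdrawal sentence adds to this, because it names only the treatment group. The protocol uses that term elsewhere for the IFC arm, so read literally the two arms could be handled differently.

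**Working it through.** **Inputs.** From Power/sample size: control mean 84.2 mg, SD 44.7 mg, 30% reduction, two-sided α = 0.05, 50 per group for 80% power, 25 per group at the start, at most 10% loss, 20 per group at the end. The size and direction of any selective loss are not in the documents and are assumed below.

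**Step 1: reproduce the plan's figure.** The target difference is 0.30 × 84.2 = 25.26 mg, so d = 25.26 / 44.7 = 0.565. The normal-approximation formula gives 50 per group, and the t-test version gives 50.1. The stated sample size reproduces.

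**Step 2: losses.** A 10% loss leaves 25 × 0.90 = 22.5 per group. Finishing with 20 is a loss of 1 − 20/25 = 20%, twice the stated maximum.

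**Step 3: power, two-sided t-test, d = 0.565.**

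| Per group | Power |
|---|---|
| 50 | 79.9% |
| 25 | 49.9% |
| 22.5 | 45.7% |
| 20 | 41.4% |

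If only the IFC arm loses 10% (25 against 22.5), power is 47.8%.

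**Step 4: illustrative bias.** Suppose k of 25 IFC patients are dropped and none in the placebo arm is lost selectively. Let the dropped patients average s SD above the mean of their whole arm. The mean of those left falls by

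b = k / (25 − k) × s × 44.7 mg.

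For k = 5 and s = 1: 5/20 × 44.7 = 11.2 mg, which is 11.2 / 25.26 = 44% of the target difference.

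**Step 5: false-positive rate.** With no true effect and the SD unchanged, the test statistic is noncentral t with n₁ + n₂ − 2 degrees of freedom and noncentrality (b / 44.7) × √(n₁n₂ / (n₁ + n₂)). The ranges take the control group either as 25 or as equal to the reduced IFC group. For k = 5, s = 1 and 25 controls: 0.25 × √(25 × 20 / 45) = 0.833, giving 12.9%.

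| k lost of 25 | s | Fall in IFC mean | Share of 25.26 mg | False-positive rate |
|---|---|---|---|---|
| 2.5 (10%) | 0.5 | 2.5 mg | 10% | 5.4% |
| 2.5 (10%) | 1 | 5.0 mg | 20% | 6.5–6.6% |
| 5 (20%) | 0.5 | 5.6 mg | 22% | 6.7–6.9% |
| 5 (20%) | 1 | 11.2 mg | 44% | 12.0–12.9% |

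In whole patients near 10%, k = 2 gives 1.9–3.9 mg and 5.2–6.0%; k = 3 gives 3.0–6.1 mg and 5.6–7.4%.

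**Step 6: how extreme is the top row?** If exactly the five highest of 25 normally distributed values were removed, they would average about 1.34 SD above the mean (simulated). A shift of 1 SD at k = 5 is therefore close to the limit.

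**The case against.** The strongest reply is that being dropped from the study describes participation, not deletion of recorded outcomes. The sentence sits in a sample-size paragraph, and the analysis section excludes nobody. That is right as far as the words go: the completers analysis is inferred. The inference is still the natural one, because the paragraph counts the study after losses and nothing elsewhere keeps the lost patients in.

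Other points stand in part:

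- **When patients are lost.** The documents do not divide losses by time or reason. The claim that the data already exist is firm for missed visits at 2 and 6 weeks. It is weaker for patients who withdraw or go home within 48 hours. That most losses would be of the first kind is a fair inference, since the protocol bases its expected loss on follow-up attendance.
- **Power.** Some early leavers would have no usable 48-hour total under any rule, so the drops from 49.9% are the most that a better rule could recover. The low starting power is a separate problem.
- **Bias.** One-sided, opioid-related loss is an assumption. A sensory placebo and only two days of device use make it less obvious, and attendance is said to be almost complete. With one patient lost of 25, the same formulas give 0.9–1.9 mg and 5.1–5.2%. Measuring the gap from retained patients, not from the whole arm, makes the 20%, 1 SD case 0.20 × 44.7 = 8.9 mg.
- **Unequal arms.** Naming only the treatment group may be loose drafting, since the next sentence speaks of patients in general. One clear sentence would settle it.

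**Conclusion.** The concern holds. As written, the rule drops randomised patients for reasons that often have nothing to do with whether their primary outcome was observed, and no section brings them back into the analysis.

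The loss of power is at most about 4 points at the stated 10% (49.9 − 45.7 = 4.2) and about 8 to 9 at the planned 20 per group (49.9 − 41.4 = 8.5). These figures assume the plan's own mean, SD and effect. The bias figures show only what the rule would allow. The 10% case, with a false-positive rate of 5.4% to 6.6%, is the one to keep in mind; 12.9% needs twice the stated maximum loss and near-extreme selection. This should be fixed before the data are seen, because the choice of who is counted is hard to defend afterwards.

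**What to change.** Replace the drop-out rule with wording to this effect:

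> All randomised patients are analysed in the group to which they were assigned, and the same rule applies to both groups. Stopping the device or missing a post-operative visit does not remove a patient. All recorded outcomes, including 24- and 48-hour opioid use from the chart, are analysed, subject to consent to use the data. Only outcomes that were not observed are missing. Exclusions and incomplete 48-hour totals are reported by arm.

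A completers analysis may be kept as secondary. Data analysis should state the same set and say in advance how incomplete 48-hour totals are handled. The expected loss should be stated consistently, since 10% and 20 of 25 do not agree.

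The cost is protocol wording and a check that the consent terms allow data to be used after withdrawal. No new collection is needed for inpatient opioid use, which nurses already chart. The change does not cure the roughly 50% power at 25 per group.
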